4. INTERIM ANALYSES AND DATA MONITORING COMMITTEE (DMC)

Interim analyses were planned for this study for regulatory submission. Interim SAP was specified separately.

5. CHANGES IN CONDUCT OR PLANNED ANALYSES FROM THE PROTOCOL

COVID-19 impact will be assessed and summarized for major protocol deviation, AE, concomitant medication, and subject disposition.

6. DEFINITIONS AND CONVENTIONS FOR HANDLING OF DATA

Dataset specifications will be provided in a separate document.

6.1. Analysis Visit Windows

Scheduled analysis visits are visits upon scheduled time points as specified in [Table 1 Schedule of Visits and Assessments](#).

Scheduled analysis visits during the study period will be the same as the nominal visits collected in the eCRF unless otherwise specified by the specification document for analysis datasets. There will be one valid value of assessment kept for each scheduled analysis visit in summary/ analysis statistics.

Unscheduled visits are visits with data not collected at scheduled time points. Unscheduled visits will not be used for by-visit summary/analysis statistics unless specified otherwise. All unscheduled visits will be included as collected in eCRF in listings.

6.2. Handling Of Concentration Data Below The Lower Limit Of Quantification

For PK analysis, individual < LLOQ values will be converted using the following rules:

- < LLOQ values will be set to "0" if before t_{max} or
- < LLOQ values will be set to "missing" if after t_{max} For Tables and Listings:
- For individual concentration values, the < LLOQ values are considered equal to 0 for the calculation of descriptive statistics, but reported as '< LLOQ' in concentration listings.
- For mean concentration values, if the mean is < LLOQ, '< LLOQ' is reported in concentration tables.
- For mean concentration-related PK parameter values (eg, C_{max} , C_{last} , etc.), if the mean is < LLOQ, the mean of the value is reported in the PK tables.

For Figures:

- For individual and mean figures, < LLOQ values are presented as 0 before the last sampling time point (t_{last}) for the linear representation (no value for semi-log plot), and are not presented after t_{last} ,

During pharmacokinetic analysis, pre-dose values that are either missing or < LLOQ will be assigned a value of zero when calculating AUC values.

PK concentration values < LLOQ will be treated as zero for the determination of summary statistics and will be treated as missing for the calculation of the geometric means. For the presentation of summary statistics, if at least 1 subject has a concentration value < LLOQ for the time point, then the minimum value will be displayed as "< LLOQ". If more than 50% of the subjects have a concentration data value < LLOQ for the time point, then the minimum and

median values will be displayed as “< LLOQ”. If all subjects have concentration data values <LLOQ for the time point, then all order statistics (minimum, median, maximum) will be displayed as “<LLOQ”. If the mean is less than the lower limit of quantification, the mean values will be displayed as “<LLOQ”.

All original values will be presented in the by-subject listings.

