 Vital signs measurements include temperature, respiratory rate, blood pressure, and heart rate. Blood pressure, respiratory rate, and heart rate will be measured after the subject has been in a seated or supine position for at least 5 minutes.

CONFIDENTIAL

The information contained herein may not be used, disclosed, or published without the written consent of Biogen MA Inc.

PK samples will be collected in a subset of De Novo Subjects at selected sites. Samples will be collected predose, and at 0.5, 1, 2, 3, 4, 6, and 8 hours after the morning dose on Days 1 and 29. Additional PK samples will be collected prior to and approximately 2 to 3 hours following the morning or evening dose on Days 15 and 57. Specifics of the study visits for PK sample collection and PK sampling procedures will be communicated with the sites outside of this protocol.

Use "Screening" version at screening; use "Since Last Visit" version at all other scheduled visits.

At Visit 2, dispense Emergency Treatment Card to De Novo Subjects and confirm possession/redispense if necessary for Rollover Subjects. At all other visits, confirm subject's possession of card and redispense if necessary.

CONFIDENTIAL

The information contained herein may not be used, disclosed, or published without the written consent of Biogen MA Inc.

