3.7. Pharmacokinetic Data Analysis

PK analyses will be performed using the PK analysis set. Individual plasma concentrations will be listed by actual sampling times and summarized by nominal sampling times using descriptive

statistics. Plots of individual and mean concentrations over nominal time will also be generated. PK parameters will be calculated using non-compartmental analysis. Parameters will be estimated using actual elapsed time from dosing, and summarized using descriptive statistics. A subject listing of individual PK parameters will be provided.

Non-compartmental analysis will be performed to estimate the PK parameters as data allow. Additionally, PK concentration data obtained from this study will may be combined with data from other studies to develop a population PK model, which will be reported separately.

The PK parameters to be calculated includes, but is not limited to:

- C_{\max} : Maximum observed concentration
- t_{\max} : Time to reach C_{\max}
- AUC_{last} : Area under the plasma concentration versus time curve calculated using the trapezoidal method from time zero to the last observed concentration above the lower limit of quantification.

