7.1. Reporting Precision

Summary statistics will be presented to the degree of precision in [Table 6](#), unless otherwise specified:

Table 6: Degree of Precision

Statistics	Degree of Precision
Mean, Geometric mean, Median, Quartiles, Confidence limit boundaries	One more than the raw data, up to 3 decimal places.
Standard deviation, Standard error	One more than the mean, up to 3 decimal places
Minimum, Maximum	The same as the raw data, up to 2 decimal places
p-value	Rounded to 3 decimal places and therefore presented as 0.xxx; p-values smaller than 0.001 as '< 0.001'; p-values greater than 0.999 as '> 0.999'.
Percentage	One decimal place. A percentage of 100% will be reported as 100%. Percentages of zero will be reported as 0.

Fractional numeric values will be presented with a zero to the left of the decimal point (for example, 0.12–0.30).

For PK concentrations and parameters the precision for summary statistics will be defined by the measurement resolution.

For weight, height, and body mass index (BMI), one decimal place will be used for summary statistics.

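### SAP 6.2 drops values below LLOQ from geometric mean concentrations and sets no display rule, so the geometric mean can never show as below LLOQ

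*SAP*

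**What the plan says.** SAP 6.2 applies two rules to the same concentrations. The general rule is "PK concentration values < LLOQ will be treated as zero for the determination of summary statistics". For geometric means the same values "will be treated as missing for the calculation of the geometric means".

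The section then sets display rules:

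- Arithmetic mean: "For mean concentration values, if the mean is < LLOQ, '< LLOQ' is reported in concentration tables".
- Minimum: shown as below LLOQ as soon as one subject is below it.
- Minimum and median: the trigger is "If more than 50% of the subjects have a concentration data value < LLOQ for the time point".
- All subjects below LLOQ: "then all order statistics (minimum, median, maximum) will be displayed as" below LLOQ.

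None of these covers the geometric mean, and no minimum number of contributing values is set for it.

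The geometric mean is evidently meant to be reported, because SAP 7.1 sets its precision in the row "Mean, Geometric mean, Median, Quartiles, Confidence limit boundaries". The general list of summary statistics in SAP 7 leaves it out, and SAP 9 places the table shells in a separate document. SAP 3.7 gives the unit of summary: "Individual plasma concentrations will be listed by actual sampling times and summarized by nominal sampling times using descriptive" statistics. Under Protocol Table 1, footnote 11, on Days 1 and 29: "Samples will be collected predose, and at 0.5, 1, 2, 3, 4, 6, and 8 hours after the morning dose". SAP 3.1.1.3 puts the PK subset at about 50 De Novo subjects.

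**The concern.** A zero cannot enter a geometric mean, so some special rule is needed. The rule chosen removes exactly the lowest values and leaves no trace of this beside the result. The statistic changes its population from one time point to the next: it describes whichever subjects were quantifiable there.

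The design makes time points with many low values plausible. The capsules contain enteric-coated delayed-release minitablets (Protocol 7.3.1), and sampling starts predose and at 0.5 and 1 hour. Day 1 predose is the clearest case. Some subjects may enter while receiving DMF (Protocol 5.2), the timing of stopping it is left to the investigator (Protocol 7.7.1.2), and MMF is the active metabolite of DMF (Protocol 3.3). A Day 1 predose geometric mean of MMF could then describe only recent DMF users while being labelled as the group's value.

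At stake is a descriptive PK table in which one measure of location reports quantifiable exposure while two others report that there was none to quantify.

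**Working it through.** The plan states no figure to reproduce. The check has a part that needs no assumption and a part that does.

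**1. Lower bound (no assumption).** The geometric mean is exp(mean of log x) over values with x ≥ LLOQ. Each log x is at least log LLOQ, so the result is at least LLOQ whenever one value is quantifiable. If every value is below LLOQ it is undefined, and SAP 6.2 does not say what to print.

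**2. When the other statistics are flagged.** Let f be the fraction below LLOQ. The arithmetic mean with zeros is (1 − f) × (mean of the quantifiable values). It is below LLOQ when the mean of the quantifiable values is less than LLOQ/(1 − f). The median is flagged when f > 0.5.

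**3. Fixed examples, n = 50, in units of LLOQ.**

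| Below LLOQ | Quantifiable values | Mean with zeros | Median | Geometric mean (SAP rule) |
|---|---|---|---|---|
| 26 | 24 at 2.0 | 24 × 2.0 / 50 = 0.96, flagged | flagged | 2.0 |
| 40 | 10 at 1.5 | 10 × 1.5 / 50 = 0.30, flagged | flagged | 1.5 |
| 49 | 1 at 3.0 | 3.0 / 50 = 0.06, flagged | flagged | 3.0, from one subject |
| 26 | 24 at 3.0 | 24 × 3.0 / 50 = 1.44, not flagged | flagged | 3.0 |

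The last row shows that the mean and median need not both be flagged.

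**4. Size under a lognormal model (assumed).** The documents give no LLOQ, CV or below-LLOQ rate, so both f and the CV are varied. With log-SD σ and z the standard normal quantile of f, the mean of log x among quantifiable values exceeds the overall mean of log x by σ × φ(z)/(1 − f). The overstatement is therefore exp(σ × φ(z)/(1 − f)). A CV of 50% gives σ = √ln(1 + 0.5²) = 0.472. A σ of 0.9 corresponds to a CV of √(exp(0.81) − 1), about 112%.

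| f | φ(z)/(1 − f) | Ratio, CV 50% | Ratio, CV 112% |
|---|---|---|---|
| 0.3 | 0.497 | exp(0.235) = 1.26 | exp(0.447) = 1.56 |
| 0.5 | 0.798 | exp(0.377) = 1.46 | exp(0.718) = 2.05 |
| 0.6 | 0.966 | exp(0.456) = 1.58 | exp(0.869) = 2.39 |
| 0.8 | 1.400 | exp(0.661) = 1.94 | exp(1.260) = 3.5 |

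**5. Simulation check (20,000 samples of n = 50 per scenario).** At CV 50%, the average geometric mean under the SAP rule against the true one is 1.402/0.887 = 1.58 at 60% below LLOQ and 1.306/0.672 = 1.94 at 80%, in agreement with the formula. At 60%, the mean and median are both flagged in 90% of samples at CV 50% and in 80% at CV 100%. At 80%, both are flagged in essentially all samples. At 30%, this almost never happens. The smallest geometric mean in any sample was 1.001 × LLOQ.

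**The case against.** The strongest reply is that little depends on this rule. PK is descriptive in about 50 subjects. Cmax, tmax and AUClast come from individual profiles, and AUC has its own below-LLOQ rules. Any population PK model is reported separately. Excluding values below LLOQ is an explicit, prespecified choice, and the flags on the minimum, median and mean already warn the reader. By-subject listings keep all original values. All of this stands, and it is why the point is minor. It does not supply the missing display rule.

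Four stronger readings are tempting, and the documents do not support them.

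- **That the plotted mean profile is inflated.** SAP 3.7 plots individual and mean concentrations, and SAP 6.2 shows values below LLOQ as zero before the last sampling time on the linear plot. Zeros pull that profile down, not up.
- **That table rows will contradict themselves.** This needs the geometric mean to be printed beside the mean and median without a count of contributing subjects. The shells are not available, so the layout is unknown. The difference between the statistics exists in any layout.
- **That the ratios apply to the earliest samples.** Before absorption, or at Day 1 predose in subjects with no fumarate on board, values below LLOQ are essentially true zeros. There is then no positive true geometric mean to divide by, and no ratio is defined.
- **That LLOQ/2 must be substituted.** That choice is also arbitrary, and for true zeros it would insert exposure that is not there.

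**Conclusion.** The point holds as a minor defect in the reporting rule. Followed as written, SAP 6.2 gives a geometric mean that is at or above LLOQ at every time point with at least one quantifiable value, including time points where the mean and median are reported as below LLOQ. That conclusion is arithmetic.

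The size is conditional. For lognormal concentrations with a CV of about 50% to 112%, the overstatement is about 1.3 to 1.6 times with 30% of values below LLOQ, 1.6 to 2.4 times with 60%, and 1.9 to 3.5 times with 80%. Both the CV range and the below-LLOQ fractions are assumptions. At 30% the bias exists, but the mean and median would normally not be flagged.

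The reach is narrow: tabulated geometric mean concentrations in the PK subset. The linear mean plots, AUClast, Cmax and the individual listings are not affected, and no safety or efficacy result depends on the rule.

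**What to change.** In SAP 6.2, add two rules.

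1. Display the geometric mean as below LLOQ (not calculated) when more than 50% of subjects are below LLOQ at a time point, including when all are. This is the trigger already used for the median.
2. At each time point, show the number of values below LLOQ and the number contributing to the geometric mean.

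The first rule removes the most misleading values and settles the undefined case. It does not correct the bias at or below the trigger, where the model above still gives up to about 1.5 to 2.1 times at 50%; the counts in the second rule make that visible. A summary with LLOQ/2 substituted could be added as an optional sensitivity display, but is not required.

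The cost is two sentences in the SAP and a programming rule, with no new data. The downside is that some geometric means are no longer printed.

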6.3. Handling of Partial Dates of Concomitant Medication

Partial start dates of prior and concomitant medications will be assumed to be the earliest possible date consistent with the partial date. Partial stop dates of prior and concomitant medications will be assumed to be the latest possible date consistent with the partial date. In the case of completely missing stop dates, medication will be assumed to be ongoing.

6.4. Safety Data Handling

All efforts should be made to obtain the missing information from the Investigator. For C-SSRS, vital signs, laboratory testing (chemistry, hematology, urinalysis), and 12-lead ECGs, only observed data will be used for analyses, and missing data will not be imputed, except for missing and partial start dates of AEs which are handled in this study as follows:

1. Missing day: If AE start year and month are same as first dose year and month of study drug then set the missing day to first dose day; Otherwise set the missing day to 1st of the month;
2. Missing both month and day: If AE start year is same as first dose year of study drug then set the missing month and day to first dose month and day; Otherwise set the missing month and day to 1st January;
3. Missing day, month, and year: Set the missing date to first dose date of study drug; Note: If the imputed AE start date is later than AE end date then AE start date is set to the AE end date.

7. GENERAL STATISTICAL METHODOLOGY

In general, summary statistics (n, mean, SD, median, minimum, and maximum for continuous variables, and number and percentage of subjects in each category for categorical variables) will be provided by treatment group. All summary tables will be based on observed data, and missing values will not be imputed unless otherwise indicated. Measurements collected from unscheduled visits or repeated assessments will not be included in the by-visit summary tables or figures, but will be included in the derivation of the last post-baseline value during treatment, the analyses for the potentially clinically significant (PCS) post-baseline values, and subject listings. Source data for the summary tables and statistical analyses will be presented as subject data listings.

7.1. Reporting Precision

Summary statistics will be presented to the degree of precision in [Table 6](#), unless otherwise specified:

Table 6: Degree of Precision

Statistics	Degree of Precision
Mean, Geometric mean, Median, Quartiles, Confidence limit boundaries	One more than the raw data, up to 3 decimal places.
Standard deviation, Standard error	One more than the mean, up to 3 decimal places
Minimum, Maximum	The same as the raw data, up to 2 decimal places
p-value	Rounded to 3 decimal places and therefore presented as 0.xxx; p-values smaller than 0.001 as '< 0.001'; p-values greater than 0.999 as '> 0.999'.
Percentage	One decimal place. A percentage of 100% will be reported as 100%. Percentages of zero will be reported as 0.

Fractional numeric values will be presented with a zero to the left of the decimal point (for example, 0.12–0.30).

For PK concentrations and parameters the precision for summary statistics will be defined by the measurement resolution.

For weight, height, and body mass index (BMI), one decimal place will be used for summary statistics.

8. PROGRAMMING SPECIFICATIONS

Programming specifications will be provided in a separate document.

9. MOCK TABLES, LISTINGS AND GRAPHS (TLGS)

Mock-up tables and listings will be provided in a separate document.

